4.4.3. Exploratory Efficacy Variables

The following exploratory efficacy variables will be analyzed.

- Association of clinical efficacy endpoints with baseline tumor biomarker parameters (PD-L1, immune cell subsets, MHC class I/II, gene expression profile and tumor mutational burden)
- In a subset of study sites: Association of clinical efficacy endpoints with post-treatment changes in frequency and clonal repertoire of HPV antigen specific T cells, peripheral blood immune cell subsets (Teff, Treg, myeloid, dendritic and NK cells) and serum cytokine levels when available
- Cemiplimab immunogenicity as measured by anti-drug antibodies (ADA) to cemiplimab
- HPV serotyping of archival tumor

4.5. Safety Variables

Patient safety will be assessed through the collection of reported adverse events (AEs), clinical laboratory data, vital signs, ECG, and physical exam.

Period of observation: The observation period will be divided into three segments: pretreatment, on-treatment, and posttreatment.

- The pretreatment period is defined as the time from signing the ICF to before the first dose of study drug.
- The on-treatment period is defined as the day from first dose of study drug to the last dose of study drug plus 90 days, or 1 day prior to starting a new treatment for cervical cancer, whichever is first.
 - The period from the first dose of ISA 101b to the first dose of cemiplimab reflects the on-treatment period associated with ISA 101b alone.
- The posttreatment period is defined as the day after the on-treatment period until 1 year after the end of the on-treatment period or the start of a new treatment for cervical cancer, whichever is first.

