4.2. Secondary Endpoints

The secondary endpoints are:

- Incidence and severity of TEAEs/adverse events of special interest (AESIs)/serious adverse events (SAEs) and \geq grade 3 laboratory abnormalities during the treatment period and up to 90 days after the last dose of study treatment
- DOR
- PFS
- OS

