8.2.3. Immune-Mediated Adverse Events

8.2.3.1. Identification of Immune-mediated Adverse Events

Investigators must be extremely vigilant and be ready to intervene early in the management of imAEs, as the onset of symptoms of imAEs (eg, pneumonitis) may be subtle. An imAE can occur at any time during treatment or several months after the last dose of treatment. All AEs of unknown etiology associated with study drug exposure should be evaluated to determine possible immune etiology. If an imAE is suspected, efforts should be made to rule out neoplastic, infectious, metabolic, toxin or other etiologic causes prior to labeling an AE as an imAE.

Based on the emerging safety profile of cemiplimab and other antibodies targeting the PD-1/PD-L1 axis, working case definitions are provided in the Investigator's Brochure to help investigators distinguish imAEs from non-immune AEs commonly associated with PD-1 inhibition ([Naidoo, 2015](#)), ([Weber, 2015](#)). This is not exhaustive of all possible imAEs. Clinical presentations of less common imAEs, including neurologic, musculoskeletal, cardiac, renal, and ocular events ([Hofmann, 2016](#)), ([Zimmer, 2016](#)), should be reviewed in patients with concerning presentations.

The case definitions in the Investigator's Brochure have not been validated and are intended only as guidance for investigators to help distinguish imAEs from non-immune AEs. These definitions may evolve as clinical experience increases with cemiplimab and other antibodies targeting the PD-1/PD-L1 axis. Investigators' clinical judgment may include other factors when determining if an AE is immune-mediated.

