10. SAFETY EVALUATION AND REPORTING

10.1. Recording and Reporting Adverse Events

10.1.1. Adverse Events

The investigator (or designee) will seek information on AEs at each patient contact, and record all AEs that occur from the time the informed consent is signed until 90 days after the last study treatment, or until the patient commences another anticancer systemic therapy, whichever comes first. After informed consent has been obtained but prior to initiation of study drug, only the following AEs should be reported:

- SAEs
- Non-SAEs caused by a protocol-mandated intervention (eg, non-SAEs related to invasive procedures such as biopsies)

Other AEs that occur prior to the first treatment should be reported on the medical history CRF.

All AEs after initiation of study treatment and until 90 days after the last study treatment, regardless of relationship to study treatment, will be reported on the AE CRF. Additionally, any SAE or other AE of concern that the investigator believes may be related to study treatment and that occurs later than 90 days after last study treatment, or after the patient has commenced another anticancer systemic therapy (whichever comes first) should be reported.

Study treatment includes cemiplimab and ISA101b.

Information on follow-up for AEs is provided in Section 10.1.2. Laboratory, vital signs, or ECG abnormalities are to be recorded as AEs as outlined in Section 10.1.5.

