4.5.1. Adverse Events and Serious Adverse Events

An AE is any untoward medical occurrence in a patient administered a study drug which may or may not have a causal relationship with the study drug. Therefore, an AE is any unfavorable and unintended sign (including abnormal laboratory finding), symptom, or disease which is temporally associated with the use of a study drug, whether or not considered related to the study drug.

The investigator (or designee) will seek information on AEs at each patient contact and record all AEs that occur from the time the informed consent is signed until 90 days after the last dose of study drug. Prior to initiation of study drug, only the following categories of AEs should be reported on the AE CRF:

- Serious Adverse Events (SAEs)
- Events associated with a protocol-mandated intervention and which are not drug related (eg, AEs related to an invasive procedure such as a biopsy)

Other AEs that occur prior to first treatment should be reported on the medical history CRF.

All AEs after initiation of study treatment and until 90 days after the last dose of study treatment or 1 day prior to starting a new treatment for cervical cancer, whichever is first, regardless of relationship to study treatment, will be reported on the AE CRF. Additionally, any SAE or AE that the investigator believes may be related to study drug(s) and that occurs later than 90 days after last dose of study drug should be reported.

Pre-treatment AEs are defined as AEs that developed during the pretreatment period and are not treatment-emergent as defined below.

Treatment-emergent AEs (TEAEs) are defined as AEs that developed or worsened during the on-treatment period and treatment-related AEs that occur during post-treatment period.

Post-treatment AEs are defined as AEs that developed or worsened during the post-treatment period and are not considered drug related by the investigator.

All AEs are to be coded to a Preferred Term (PT) and associated primary System Organ Class (SOC) according to the latest version of Medical Dictionary for Regulatory Activities (MedDRA).

A SAE is an AE that is classified as serious according to the criteria specified in the protocol.

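### Related adverse events that begin after new anticancer therapy fall in no SAP observation period and in none of the SAP's TEAE-based tables

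*SAP*

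**What the plan says.** **Periods.** SAP 4.5 recognises three and no others: "The observation period will be divided into three segments: pretreatment, on-treatment, and posttreatment". On-treatment ends 90 days after the last dose "or 1 day prior to starting a new treatment for cervical cancer, whichever is first". Post-treatment begins the next day and runs "until 1 year after the end of the on-treatment period or the start of a new treatment for cervical cancer, whichever is first".

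**Treatment-emergent events.** SAP 4.5.1 defines TEAEs as "AEs that developed or worsened during the on-treatment period and treatment-related AEs that occur during post-treatment period". Its separate category of post-treatment AEs is limited to events in that period that the investigator considers unrelated.

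**Tables.** SAP 5.8.1 puts its whole list of AE tables under a TEAE lead-in. The imAE row and the fatal-event row are also explicitly treatment-emergent.

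**Collection.** Protocol 10.1.1 says that related SAEs and other related AEs of concern arising more than 90 days after treatment, "or after the patient has commenced another anticancer systemic therapy (whichever comes first) should be reported". Protocol 10.1.2 repeats the duty. Neither section sets an end date.

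**Protocol analysis text.** Protocol 11.4.5.1 cuts the on-treatment period at new cervical cancer treatment too. It names the same two post-treatment end points, without saying that the earlier one applies, and restricts TEAEs to the on-treatment period. Protocol 11.4.5.2 plans a summary of deaths and other SAEs.

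**The concern.** By adding late related events to its TEAE definition, the SAP shows that it means to tabulate them. The new-treatment cut then removes them for any patient who has moved on. For events inside the one-year limit, whether a related event is tabulated depends only on whether the next therapy has begun, not on its cause or its timing relative to study drug.

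This matters because the protocol's main identified risk can appear late: "An imAE can occur at any time during treatment or several months after the last dose of treatment" (protocol 8.2.3.1). SAP 4.4.2 itself expects many patients to receive new anticancer therapy after progression. Safety is a secondary objective of a single-arm study of 105 patients, so a handful of related serious events missing from the tables would change the picture a reader takes from them.

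**Working it through.** The plan states no figure to reproduce; the check is date logic.

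**Inputs.** Day 0 is the last dose and d is the day on which new cervical cancer treatment starts. The period bounds come from SAP 4.5, one year is taken as 365 days, and each end day counts as inside its period.

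**Formulas.**
- On-treatment ends at E = min(90, d − 1), or at 90 if there is no new treatment.
- Post-treatment runs from E + 1 to min(E + 365, d), or to E + 365 if there is no new treatment.
- A related event is a TEAE if it falls in either period.

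| d | On-treatment ends | Post-treatment | Length (days) | Related event with onset on |
|---|---|---|---|---|
| none | 90 | 91–455 | 365 | 120, 200 or 400: TEAE |
| 30 | 29 | 30–30 | 1 | 45, 75 or 120: no period |
| 60 | 59 | 60–60 | 1 | 75 or 120: no period |
| 91 | 90 | 91–91 | 1 | 120: no period |
| 150 | 90 | 91–150 | 60 | 120: TEAE; 200: no period |
| 300 | 90 | 91–300 | 210 | 200: TEAE; 400: no period |

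For any d up to 91, E = d − 1 and the post-treatment period runs from d to min(d − 1 + 365, d) = d, which is one day.

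**Example.** New therapy starts on day 40 and a related pneumonitis begins on day 60. On-treatment ended on day 39 and post-treatment was day 40 only. The event is therefore neither a TEAE nor a post-treatment AE, and it enters no table in SAP 5.8.1. If it is an SAE or an AE of concern, protocol 10.1.1 requires it to be reported. Had it begun on day 35 and proved fatal later, it would remain a TEAE; the gap concerns onset or worsening after the switch.

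**Could the SAP sentence be read differently?** It might mean one year after whichever comes first: the end of on-treatment or the start of new treatment. But on-treatment always ends before new treatment starts, so the closing words of "until 1 year after the end of the on-treatment period or the start of a new treatment for cervical cancer, whichever is first" would then do no work. The reading used here is the natural one.

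**Size per event.** If all 105 planned patients are treated, one omitted patient changes an incidence by 1/105 = 0.95 percentage points.

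**The case against.** The best counter-argument is that a new-therapy cut is ordinary practice. After the switch, full AE recording stops and reports arrive only if the investigator happens to learn of an event. Those reports are also confounded by the next drug. This is a sound reason to keep the cut for unrelated events and not to pool late related events with the main columns. It is not a reason to have no table for them.

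Several stronger readings are tempting, but the documents do not support them:

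- **That these events are collected and then never reported.** Protocol 10.4 promises all safety observations in the study report, protocol 11.4.5.2 plans a summary of deaths and other SAEs, and OS counts every death. What is missing is a SAP table for the related events.
- **That the SAP alone is at fault.** Protocol 11.4.5.1 has similar bounds and a narrower TEAE definition than the SAP.
- **That the cut plainly contradicts the secondary endpoint**, which protocol 4.2 describes as running "during the treatment period and up to 90 days after the last dose of study treatment". That endpoint includes TEAEs, and protocol 5.3 defers to Section 11.4 for definitions, where the cut appears. At most, its SAE and AESI components can be read as uncut.
- **That most patients are affected.** SAP 4.4.2 says only that many may receive new therapy, and protocol 8.8 allows treatment beyond progression, which can delay a switch.

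**Conclusion.** The gap is real and follows from the definitions alone. Related SAEs and other related AEs of concern that start or worsen after new therapy begins must be reported, yet they have no SAP period and no TEAE-based table, including the imAE and fatal-TEAE tables. The deaths are counted elsewhere; the related events behind them are not tabulated.

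The number of patients affected cannot be computed, because the documents give neither a time to next therapy nor a rate of late related events. A reader might try to size the loss by the share of the 90-day window cut off. That would measure all-cause observation time under assumed inputs, not lost related events, and should not be used. The direction is clear for the tables concerned: omission can only lower their counts of related events. That does not show that the safety endpoint as a whole is materially biased. The conclusion rests on the natural reading of SAP 4.5 and on SAP 5.8.1 being the full list of planned AE tables. The change should be made; the primary ORR analysis is untouched.

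**What to change.** 1. Add one rule to SAP 4.5 and 4.5.1: related AEs and SAEs reported after the start of new anticancer therapy are assigned to the post-treatment period for analysis.
2. In SAP 5.8.1, show them in a separate column or table by SOC, PT and grade. Identify related deaths, imAEs and events within 90 days of the last dose.
3. Keep the existing cut for unrelated events.
4. Align protocol 11.4.5.1 with the rule, or record the difference in SAP 1.2.4, which at present lists only added efficacy endpoints.

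**Cost.** SAP wording and one extra column or table, built from events that protocol 10.1.1 and 10.1.2 already require to be reported. SAP 1 allows revision before database lock. The drawback is that some of these events will be confounded by the new therapy and incompletely ascertained; keeping them in a separate column makes that visible.

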4.5.1. Adverse Events and Serious Adverse Events

An AE is any untoward medical occurrence in a patient administered a study drug which may or may not have a causal relationship with the study drug. Therefore, an AE is any unfavorable and unintended sign (including abnormal laboratory finding), symptom, or disease which is temporally associated with the use of a study drug, whether or not considered related to the study drug.

The investigator (or designee) will seek information on AEs at each patient contact and record all AEs that occur from the time the informed consent is signed until 90 days after the last dose of study drug. Prior to initiation of study drug, only the following categories of AEs should be reported on the AE CRF:

- Serious Adverse Events (SAEs)
- Events associated with a protocol-mandated intervention and which are not drug related (eg, AEs related to an invasive procedure such as a biopsy)

Other AEs that occur prior to first treatment should be reported on the medical history CRF.

All AEs after initiation of study treatment and until 90 days after the last dose of study treatment or 1 day prior to starting a new treatment for cervical cancer, whichever is first, regardless of relationship to study treatment, will be reported on the AE CRF. Additionally, any SAE or AE that the investigator believes may be related to study drug(s) and that occurs later than 90 days after last dose of study drug should be reported.

Pre-treatment AEs are defined as AEs that developed during the pretreatment period and are not treatment-emergent as defined below.

Treatment-emergent AEs (TEAEs) are defined as AEs that developed or worsened during the on-treatment period and treatment-related AEs that occur during post-treatment period.

Post-treatment AEs are defined as AEs that developed or worsened during the post-treatment period and are not considered drug related by the investigator.

All AEs are to be coded to a Preferred Term (PT) and associated primary System Organ Class (SOC) according to the latest version of Medical Dictionary for Regulatory Activities (MedDRA).

A SAE is an AE that is classified as serious according to the criteria specified in the protocol.

The severity of AEs (including test findings classified as AEs) will be graded using the current National Cancer Institute-Common Terminology Criteria for Adverse Events (NCI-CTCAE) grading system (v5.0). Adverse events not listed in the NCI-CTCAE v5.0 will be graded according to the following scale:

- 1 (Mild): Mild AE (minor; no specific medical intervention; asymptomatic laboratory findings only, radiographic findings only; marginal clinical relevance)
- 2 (Moderate): Moderate AE (minimal intervention; local intervention; noninvasive intervention [packing, cautery])
- 3 (Severe): Severe and undesirable AE (significant symptoms requiring hospitalization or invasive intervention; transfusion; elective interventional radiological procedure; therapeutic endoscopy or operation)
- 4 (Life-threatening): Life-threatening or disabling AE (complicated by acute, life threatening metabolic or cardiovascular complications such as circulatory failure, hemorrhage, sepsis. Life-threatening physiologic consequences; need for intensive care or emergent invasive procedure; emergent interventional radiological procedure, therapeutic endoscopy or operation)
- 5 (Death): Death associated with an AE.

The relationship of AEs to study drugs will be assessed by the investigator and be determined based on protocol specified criteria.

Laboratory results, vital signs, or ECG abnormalities are to be recorded as AEs if they are medically relevant: for example, symptomatic, requiring corrective therapy, leading to treatment discontinuation and/or fulfilling a seriousness criterion.

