11.4.5.1. Adverse Events

Definitions

For safety variables, 3 observation periods are defined:

- The pretreatment period is defined as the time from signing the ICF to before the first dose of study drug.
- The on-treatment period is defined as the day from first dose of study drug to the last dose of study drug plus 90 days, or 1 day prior to starting a new treatment for cervical cancer, whichever is first.
- The posttreatment period is defined as the day after the on-treatment period until 1 year after the end of the on-treatment period or the start of a new treatment for cervical cancer.

Treatment-emergent adverse events are defined as those that are not present at baseline or represent the exacerbation of a pre-existing condition during the on-treatment period.

Analysis

All AEs reported in this study will be coded using the Medical Dictionary for Regulatory Activities (MedDRA®).

Summaries of all TEAEs by treatment group will include:

- The number (n) and percentage (%) of patients with at least 1 TEAE by SOC and PT
- TEAEs by severity (NCI-CTCAE, version 5.0 grade), presented by SOC and PT
- Treatment-related TEAEs, presented by SOC and PT
- Treatment-emergent AESIs (defined with a PT or a prespecified grouping)

11.4.5.2. Deaths, other SAEs, and TEAEs leading to permanent treatment discontinuation will be summarized. Other Safety**Vital Signs**

Vital signs (temperature, pulse, blood pressure, and respiration rate) will be summarized by baseline and change from baseline to each scheduled assessment time with descriptive statistics.

Laboratory Tests

Laboratory test results will be summarized by baseline and change from baseline to each scheduled assessment time with descriptive statistics.

Number and percentage of patients with a potentially clinically significant value (PCSV) will be summarized for each clinical laboratory test.

Shift tables based on baseline normal/abnormal and other tabular and graphical methods may be used to present the results for laboratory tests of interest.

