1.2.4. Modifications from the Statistical Section in the Final Protocol

TTR, DCR, and dDCR were added as secondary endpoints.

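### SAP 4.5.1 counts treatment-related events from after the on-treatment period as TEAEs, against protocol 4.2 and 11.4.5.1, and SAP 1.2.4 does not declare the change

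*SAP*

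**What the plan says.** **Protocol.** Section 4.2 makes the incidence and severity of TEAEs, AEs of special interest (AESIs), SAEs and grade 3 or higher laboratory abnormalities a secondary endpoint, observed "during the treatment period and up to 90 days after the last dose of study treatment". Section 11.4.5.1 runs the on-treatment period from "first dose of study drug to the last dose of study drug plus 90 days", with an earlier end on the day before a new cervical cancer treatment. TEAEs there are events absent at baseline, or those that "represent the exacerbation of a pre-existing condition during the on-treatment period". The same section defines a one-year post-treatment period but assigns no TEAEs to it.

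**SAP.** Section 4.5 keeps the protocol's on-treatment period and lets the post-treatment period run "until 1 year after the end of the on-treatment period or the start of a new treatment for cervical cancer, whichever is first". Section 4.5.1 counts as TEAEs the events that start or worsen on treatment and, in addition, "treatment-related AEs that occur during post-treatment period". Late events that are "not considered drug related by the investigator" go into a separate post-treatment category that is not part of the TEAE count.

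**Declaration.** SAP 1.2.4 reads in full: "TTR, DCR, and dDCR were added as secondary endpoints". The revision history in SAP 1.2.5 does not mention the TEAE definition either.

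**The concern.** TEAE incidence is a named secondary endpoint, and the two governing documents would produce different tables for it. A programmer following the SAP would report something other than the protocol's endpoint, and nothing in the SAP would alert a reader of the study report.

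The SAP count also mixes two kinds of data. Up to 90 days after the last dose, all events are sought at each contact whatever their cause. After that, protocol 10.1.1 asks only for "any SAE or other AE of concern that the investigator believes may be related to study treatment", and protocol 10.1.2 covers the later SAEs that the investigator happens to be told about. Late membership in the count thus depends on an open-label causality call and on passive reporting.

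The SAP is also uneven within this one endpoint. Protocol 4.2 places adverse events and laboratory abnormalities in the same window. SAP 5.8.2 keeps worst laboratory values to the on-treatment period, while the SAP's TEAEs go beyond it. SAP 5.10.2 refers to a TEAE period, which under SAP 4.5.1 is no longer a single period.

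**Working it through.** The documents give no figure that depends on the TEAE definition, so there is nothing of the plan's own to reproduce. The check is a comparison of the definitions, followed by the arithmetic that they imply.

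**Step 1: classify an event that starts or worsens after first dose.**

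| Onset | Investigator attribution | Protocol 11.4.5.1 | SAP 4.5.1 |
|---|---|---|---|
| On-treatment | related | TEAE | TEAE |
| On-treatment | unrelated | TEAE | TEAE |
| Post-treatment | related | not a TEAE | TEAE |
| Post-treatment | unrelated | not a TEAE | not a TEAE |

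The definitions differ in one cell only, and that cell contains related events alone.

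**Step 2: the longest possible window.** Inputs are 90 days (protocol 11.4.5.1) and one year (SAP 4.5). For a related event the maximum is 90 + 365 = 455 days after last dose, against 90 days for an unrelated one. This is a ceiling. If a new cervical cancer treatment starts within 90 days, the on-treatment period ends the day before and the post-treatment period closes at that start, so almost nothing is added.

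**Step 3: direction.** SAP 5.8.1 reports patients with at least one event, and SAP section 5 takes the analysis population as denominator. Let N be that population, b the patients in a given row under the protocol definition, and m those who enter the row only through a late related event. The protocol percentage is b/N and the SAP percentage is (b + m)/N. Since m is zero or more, the SAP figure is never lower.

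**Step 4: size per patient.** Taking N = 105 (SAP 2.2, assuming all planned patients are dosed), each such patient adds 1/105 = 0.95 points.

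**Step 5: where it could show.** The values of b and m below are assumptions for illustration; the documents supply none.

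- *Low-count row*, such as grade 3 or higher, serious or immune-mediated events, with b = 10: 10/105 = 9.5%. With m = 3 it becomes 13/105 = 12.4%; with m = 5, 15/105 = 14.3%.
- *Any-grade related row.* Protocol 1.3.2 reports injection site reactions in about 85 to 90% of patients at this ISA101b dose. If that recurs and the reactions are called related, about 89 or 94 of 105 patients are already counted. At most 16/105 = 15.2 or 11/105 = 10.5 points could be added, and only if every remaining patient had a late related event. These are bounds, not estimates.

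**The case against.** The best defence is that counting late related events is the more inclusive safety choice. Protocol 10.1.3 and SAP 4.5.2 both say that immune-mediated events can appear months after the last dose. SAP 5.8.1 builds its immune-mediated, discontinuation and death tables on treatment-emergent events, so removing the clause with nothing in its place would push late related events out of those tables. The causality filter also begins in the protocol's own late data collection, and the summaries are descriptive with no hypothesis attached. All of this stands. It supports reporting the late events; it does not support merging them, undeclared, into an endpoint that the protocol limits to 90 days.

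The defence also limits what may be claimed:

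- A reader might infer that the related share of all TEAEs is biased upward. No such ratio is planned: the tables give percentages of patients in the full analysis set.
- A reader might put a number on the extra patients. The documents give no late-event rate. A patient with a late event may already be in the row, and not every late related event is an AESI or immune-mediated.
- A reader might take 455 against 90 days as a fivefold gain in events. Scheduled AE assessment stops at the 90-day safety visit, and later reporting is selective.
- A reader might say that the rates cannot be compared with other cemiplimab trials. Neither document gives those trials' TEAE definitions.
- Protocol 4.2 and 11.4.5.1 are not identical: only the latter stops at new cervical cancer treatment.

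**Conclusion.** The point holds as an explicit, undeclared conflict between the current protocol and the current SAP over the definition of a secondary safety endpoint. The direction is certain by construction: relative to the protocol definition, patient percentages for related, serious, grade 3 or higher and immune-mediated events can rise or stay level, never fall. The unit of change is 0.95 points per patient counted only through a late event, assuming a full analysis set of 105. The total cannot be derived and may be small, particularly in the any-grade related row. Low-count rows are the most exposed. The objective response rate and any decision based on it are unaffected. The change should be made before database lock, but it does not threaten the primary result.

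**What to change.** In SAP 4.5.1, define TEAEs by the on-treatment period as in protocol 11.4.5.1. Add a separate table of treatment-related AEs from the post-treatment period, including immune-mediated events, SAEs and deaths.

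If the sponsor keeps the wider definition, three things are needed: align protocol 4.2 and 11.4.5.1 with it, declare it in SAP 1.2.4, and show on-treatment-only counts beside the wider ones.

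The first route costs one SAP sentence and one extra table, and no safety information is lost. The second also needs a protocol amendment. SAP section 1 allows revision up to database lock.

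Under either route, state whether the 90-day limit in protocol 4.2 also ends at new cervical cancer treatment, and reword the reference to a TEAE period in SAP 5.10.2 to match.
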